Health Status: The *Cumulative Illness Rating Scale (CIRS)*^{135,136} was designed for use with frail nursing facility residents. CIRS will be obtained at baseline. It contains ratings of both illness severity and comorbidity. Residents are evaluated based on 13 organs or systems and a psychiatric/behavioral rating. CIRSSs ratings correlated with medication use and predicted mortality, hospitalization and disability.^{135,136}

Facility and Staff RE-AIM Measures

The Environment Assessment (Effectiveness; Adoption; Maintenance): includes 24 items that impact care of residents with BPSD (e.g., outdoor spaces are available). Items are scored as present or not present and summed. There was prior evidence of inter-rater reliability and validity based on hypothesis testing.^{8 22,23,137}

Policy Assessment (Effectiveness; Adoption; Maintenance): includes 24 items that reflect policies that support behavioral approaches for BPSD (e.g., policies on use of restraints). Items are scored as present or not present and summed. There was prior evidence of inter-rater reliability and validity.^{8 22,23,137}

The Care Plan Checklist for Evidence of Person Centered Approaches for BPSD (Effectiveness; Adoption; Maintenance) is used to evaluate care plans for approaches that address common BPSD (apathy, agitation, inappropriate/disruptive vocalizations, aggression, wandering, repetitive behaviors, resistance to care, and sexually inappropriate behaviors).

Knowledge of Behavioral Interventions For BPSD Test (Implementation; Receipt) is a 10-item multiple choice test that evaluates staff knowledge. Evidence of test-retest reliability was supported with correlations of .92 and validity with significant associations between knowledge and use of behavioral interventions for BPSD.¹³⁸

Use of Behavioral Interventions for BPSD (Implementation; Enactment) is a reliable and valid 8-item observation measure that assesses if nursing assistants implement appropriate interventions to prevent or manage BPSD when interacting with a resident during routine care.¹³⁸

Resident RE-AIM Measures

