The hypothesis will be tested by evaluating the interaction term for each outcome variable. Similar LMMs will be used to compare changes in facility level measures (i.e., environments, policies) from baseline to 12 months with only facility included as random effects. For each hypothesis, exploratory analyses will be performed to assess model assumptions. Post-analysis diagnostic measures (e.g., residuals) will be explored to assess model fit. All tests will use a 5% significance level. The use of LMM will provide flexibility with regard to assumptions related to the covariance structure of the residuals and the presence of missing data for the repeated measures.¹⁵⁴ Missing data. In prior research we had 20% rate of attrition at the resident level and 10% of facilities.^{22,23} If there is significant dropout, we will identify baseline characteristics that differ between persons or facilities that drop out. Maximum likelihood methods will be used for primary analyses, which address non-informative dropout (missing at random [MAR]). If "informative" dropout appears possible, we will consider sensitivity analyses that involve adding these relevant baseline covariates to make the MAR assumption more plausible.¹⁵⁵ Qualitative data will be collected to inform effectiveness outcomes.

Adoption: Staff Adoption: Descriptive statistics will be done to evaluate the number of Internal Champions and Stakeholder team members participating in initial face-to-face training and monthly meetings among the 25 facilities randomized to EIT-4-BPSD. We will also consider improvement in scores on the Use of Behavioral Interventions for BPSD measure at each testing time point as evidence of adoption among staff. Facility Adoption: Facility adoption will be based on changes in environments, policies, and care plans of residents at 4 and 12 months post implementation of EIT-4-BPSD such that there is at least 1 item changed in each assessment area. Further we will describe differences among EIT-4-BPSD facilities that demonstrate adoption (based on changes in environments, policies and care plans) early (the first 4 months) versus late adopters (between 5-12 months) versus those that are non-adopters (no change by 12 months). Predictors such as facility characteristics will be compared across the three potential times of adoption (early, late, nonadopters).

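### Comparing facility characteristics only across adoption classes cut at one item per area, in at most 25 homes, can cost this exploratory analysis substantial power; a regression on uncut change should be added

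*Combined protocol and SAP*

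**What the plan says.** The Adoption paragraph (Data Analysis, Aim 1) defines facility adoption by change in environments, policies and care plans at 4 and 12 months, "such that there is at least 1 item changed in each assessment area". Homes that get there in the first 4 months are early adopters and those that do so in months 5-12 are late. The third group is "those that are non-adopters (no change by 12 months"). Facility characteristics are then compared: "Predictors such as facility characteristics will be compared across the three potential times of adoption (early, late, nonadopters"). No test, model or power figure is attached. The comparison is introduced in descriptive terms: "Further we will describe differences among EIT-4-BPSD facilities that demonstrate adoption". The same paragraph counts participation "among the 25 facilities randomized to EIT-4-BPSD", so 25 is the ceiling.

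Facility and Staff RE-AIM Measures describes the scales behind the cut. The Environment Assessment "includes 24 items that impact care of residents with BPSD" and the Policy Assessment "includes 24 items that reflect policies that support behavioral approaches for BPSD"; for both, "Items are scored as present or not present and summed". No summed score is described for the Care Plan Checklist, but H2 and the Maintenance paragraph express care plans as a percentage of residents.

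Uncut facility scores are analysed elsewhere by linear mixed models, for the arm comparison (Effectiveness) and for change to 24 months (Maintenance). Neither analysis is aimed at predictors of adoption.

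**The concern.** A home that gains one item in each area and a home that gains ten can fall in the same class, while one item in one area can move a home between classes. The comparison therefore ignores most differences in the amount of change between homes on the same side of the cut. With at most 25 homes there is little information to spare.

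The adoption classes are the only quantitative route in the plan to the question of which kinds of home take the programme up; the comparison of willing and unwilling homes concerns Reach. A characteristic that truly goes with uptake could be reported as showing no difference across classes, although data already due to be collected would have shown a gradient more often.

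**Working it through.** **The plan's nearest figure.** No power is stated for the predictor comparison. Sample Size gives effect size 0.9 and power above .90 for environment and policy between arms, with 50 homes. With 25 per arm, a single-endpoint z test gives Φ(0.9 × √12.5 − 1.96) = Φ(1.222) = 0.889. Borrowing the resident-level correlation of 0.6 between repeated measures, the SD of change is √(2 × 0.4) = 0.894, and power is Φ(0.9/0.894 × √12.5 − 1.96) = 0.945. ANCOVA gives 0.978. The stated figure is reproduced under a baseline-adjusted analysis. It concerns the arms, not predictors within one arm.

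**Inputs for the predictor comparison.**
- From the plan: 25 homes (25 × 0.9 = 22.5, about 22, after the 10% facility attrition it cites), the one-item rule in all three areas, and a 5% level.
- Assumed: mean gain 0.9 SD by month 12 (the between-arm figure, borrowed as a within-arm gain and applied to all three areas) and half of it by month 4; SD of change 3 items; areas correlated ρ = 0.3 or 0.6; month-4 and month-12 change correlated 0.6; the characteristic correlated r with the part of change shared by the areas. Change is taken as gain, and homes changing in only one or two areas are counted as non-adopters.

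**Uncut scores by formula.** The characteristic correlates r√ρ with one area's change and r√ρ / √((1 + 2ρ)/3) with the mean of three. Approximate power at correlation q is Φ(atanh(q) × √(n − 3) − 1.96). For r = 0.5, ρ = 0.6, n = 25:
- one area: q = 0.5 × 0.775 = 0.387; 0.409 × 4.690 − 1.96 = −0.04; power 0.48.
- composite: q = 0.387/0.856 = 0.452; 0.488 × 4.690 − 1.96 = 0.33; power 0.63.
- with 22 homes (√19 = 4.359): 0.409 × 4.359 − 1.96 = −0.18, power 0.43; and 0.488 × 4.359 − 1.96 = 0.17, power 0.57.

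**All approaches by simulation** (25 homes, 2,000-3,000 runs per setting, whole-item changes, three-area rule):

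| Setting | ANOVA, 3 classes | Ordered test, 3 classes | One area, uncut | Any of 3 areas, Bonferroni | Composite |
|---|---|---|---|---|---|
| r = 0.5, ρ = 0.3 | 0.18 | 0.22 | 0.27 | 0.33 | 0.47 |
| r = 0.5, ρ = 0.6 | 0.29 | 0.35 | 0.48 | 0.55 | 0.64 |
| r = 0.6, ρ = 0.6 | 0.42 | 0.48 | 0.65 | 0.72 | 0.82 |

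With no association, rejection rates were 4-6%. At r = 0.3 all approaches lie between 0.13 and 0.27.

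Against the ANOVA, scores on their own scales gain between 0.27 − 0.18 = 0.09 and 0.72 − 0.42 = 0.30. A composite gains between 0.47 − 0.18 = 0.29 and 0.82 − 0.42 = 0.40. Against the ordered test, one area gains 0.05 to 0.17 and Bonferroni 0.11 to 0.24.

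**Dependence on the split.** Cutting a single normal score into three classes keeps 79% of its information with equal thirds, about 70% with a 60/30/10 split, about 51% with 80/12/8 and about 35% with 90/6/4. In the 0.9 SD setting above (ρ = 0.6) the split is near balanced: about 28% early, 34% late and 38% non-adopters. If the mean gain were 2.5 SD (r = 0.5, ρ = 0.6), power would be 0.17 for ANOVA and 0.19 for the ordered test against 0.65 for the composite, with one non-adopter or none in 90% of runs.

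**The case against.** The strongest reply is that this is a descriptive, secondary comparison. The plan introduces it as describing differences, names no test, and rests neither H2 nor maintenance on the classes. Drivers and barriers are also studied through focus groups and brainstorming. That stands and limits the importance of the point.

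The plan also asks when homes adopt, as well as how much they change. A regression on 12-month change drops timing, and the simulation ties the characteristic to amount of change, which favours the regression. If the characteristic acted as strongly on month-4 change as on month-12 change, the class tests would do better than the table shows, and an ordered test could come level with a single area's score. This too stands; it is why the classes should stay and the regression be added.

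A reader might infer that the cut discards most of the information, or that it halves power as a rule. The documents do not support either. They give no class split and no test; balanced classes keep about 79% of a single score's information, and most is lost only when more than about 80% of homes fall in one class. Nor do they support expecting an almost empty non-adopter class, which needs a much larger gain than 0.9 SD. The largest gains in the table belong to a composite that the plan does not define. Using the three measures separately gains less and brings multiplicity.

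Finally, at r = 0.3 no analysis of 25 homes is informative. True, but that is no reason to give up more power.

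**Conclusion.** The point holds as a modest one. The only planned quantitative comparison of facility characteristics with adoption uses classes cut at one item per area, and no uncut predictor analysis is planned. In the settings tabulated, the three-class comparison had lower power than uncut change, whether tested unordered or ordered: 9-30 percentage points below scores on their own scales when an unordered test is used, and more against a composite. These sizes rest on assumed predictor strength, area correlations, SD, a borrowed mean gain and a model for month-4 change, so they show that the loss can be substantial but do not estimate it for this trial. The effectiveness conclusions are unaffected, and even the better analysis remains exploratory with 25 homes or fewer.

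**What to change.** Add to the Adoption paragraph an exploratory regression of each EIT-4-BPSD home's baseline-to-12-month change on facility characteristics. The outcomes would be the environment score, the policy score and the percentage of residents with person-centered care plans, with multiplicity across the three acknowledged, or one standardised composite specified in advance. Keep the early, late and non-adopter classes to describe timing, and treat them as ordered if they are tested.

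The cost is a few sentences and a few extra regressions. They need only baseline and 12-month facility data, which Design and Procedure for Assessing Outcomes already schedule. The early/late split also needs 4-month facility change, which those two sections do not list for these measures (Appendix E, which sets timing, is not among the documents). The downside is that timing is described rather than serving as the main predictor test.

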A number of pathophysiological, psychological and environmental mechanisms likely underlie BPSD.³⁹⁻⁴⁴ From a clinical perspective, BPSD have been conceptualized as expressions of un-met needs and frustrated goals⁴⁵⁻⁴⁸ and are exhibited by up to 90% of residents with dementia.^{2,49} BPSD contribute to poor quality of life, more rapid cognitive and physical decline⁵⁰ and put residents at risk for inappropriate use of antipsychotics as well as other psychotropic medications (antidepressants, anxiolytics, sedative/hypnotics)⁵¹ and physical or environmental restraints that reduce function.^{5,2,49} The use of psychotropic medications among individuals with dementia is associated with a more rapid physical and cognitive decline than would otherwise be anticipated and with little or no improvement in BPSD.⁵¹ Behavioral approaches have repeatedly been endorsed by geriatric organizations as the first line of treatment for BPSD.⁵² Unfortunately the up-take of behavioral approaches is low. Between 2004 and 2011 fewer than 2% of nursing homes implemented these approaches.¹⁵ In 2011 approximately 25% of residents residing in nursing homes were receiving antipsychotics and 88% of these individuals had dementia.⁵³ Since then there has been a 22% decrease in use of antipsychotics to a national prevalence of 19% of residents receiving psychotropic medications in 2015.³⁷ In September 2014, the National Partnership set new goals of an additional 25% reduction in antipsychotic use by the end of 2015, and 30% reduction by 2016.⁵⁴ Further, CMS has focused regulatory oversight on ensuring that care for residents with dementia is person-centered. Due to lack of knowledge, beliefs and motivation, staff in nursing homes are ill-prepared to replace psychotropic use with person-centered care approaches.^{17,18,45} We focus this application on helping staff address the CMS mandate to implement behavioral approaches for BPSD. We will test an implementation strategy for addressing BPSD in nursing homes, which has been identified as a research priority.⁵⁵⁻⁵⁸

[figure not shown]

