Real World Experience and Pilot Testing EIT-4-BPSD: Our team has expertise with regard to clinical work ([name], [name], [name]), administration ([name]) and regulations ([name]), and implementation of relevant innovative approaches to care (all investigators) in nursing homes. In addition, we have expertise in the education of minorities and nursing assistants([name], [name], [name], [name], [name]) and using qualitative methods ([name], [name], [name]) (see biosketches). We have pilot tested the EIT-4-BPSD in two facilities (one in Maryland and one in Pennsylvania) for feasibility and demonstrated that sites are willing to identify a Champion and Stakeholder team, engage in monthly face-to-face meetings (100% participation of stakeholders) and weekly email interactions (100% participation). We implemented all components of the intervention, recruited residents (recruitment rate of 50%) and completed measures without being burdensome to residents or staff. Building on our extensive preliminary work we will test EIT-4-BPSD in 50 nursing homes in Maryland and Pennsylvania.

Methods

Design: To achieve our Aims we will use a Hybrid III pragmatic cluster randomized clinical trial³² for two reasons: (a) implementation of EIT-4-BPSD requires a facility-wide approach; and (b) we need to prevent treatment contamination that might occur if we randomized within sites. Fifty nursing homes will be randomized to treatment (EIT-4-BPSD) or Education-Only Control (EO) using permuted-block randomization. Assignment will be concealed until after the facility consents to participate. Outcomes at the resident and facility level will be evaluated. Resident outcomes will be obtained at baseline, 4 and 12 months post implementation of the intervention. Facility outcomes will be obtained at baseline and 12 months post initial implementation. We will also examine Maintenance in EIT-4-BPSD facilities at 24 months post implementation.

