Maintenance: Long term Attrition: We will track facilities that withdraw from the study within 12 months (as well as reasons for attrition). We will compare EIT-4-BPSD facilities with EO facilities to determine if there is a differential rate of attrition. Maintenance of environment and policy changes and inclusion of person-centered approaches for BPSD in care plans will be examined at 24 months post implementation of EIT-4-BPSD. Evidence of maintenance will be based on maintaining or improving Environment and Policy assessments and percentage of residents with evidence of person-centered approaches for management or prevention of BPSD in their care plans. LMMs will be used to compare changes in facility level measures from baseline to 24 months with facility included as random effects. Time will be included and recorded accordingly. Comparison of outcomes at 12 and 24 months will be examined to determine maintenance over that time period.

Primary Aim 2: Evaluation of the Feasibility, Utility and Cost in EIT-4-BPSD Facilities

Using descriptive and qualitative data from focus groups (held following the intervention) we will evaluate use of the EIT strategy and our participatory implementation process with the stakeholder team and additional facility staff. We will determine the cost of the implementation process using an activity-based costing method.

Aim 2: To evaluate the use of EIT and our participatory implementation process.

Findings will be descriptive and considered at the individual facility level and across all treatment facilities. Data will include a summary of information obtained during the intervention including: (1) ideas generated from the Brainstorming sessions¹⁵⁶; (2) themes identified in the Affinity Diagrams; and (3) "drivers" identified to overcome challenges to implementing person-centered behavioral approaches to BPSD via implementation of the EIT-4-BPSD (Interrelationship Diagraphs). We will quantify similarities across facilities to note the most common themes and drivers identified and establish best practices. We will also have facilities evaluate their goal achievement at 12 months (Appendix B).

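### The Maintenance criterion does not require a 12-month gain, its named model does not measure retention, and the 12-versus-24-month comparison has no margin

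*Combined protocol and SAP*

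**What the plan says.** The Maintenance paragraph (Data Analysis, Aim 1) opens with the intent: "Maintenance of environment and policy changes and inclusion of person-centered approaches for BPSD in care plans will be examined at 24 months". The criterion follows: "Evidence of maintenance will be based on maintaining or improving Environment and Policy assessments", together with the percentage of residents whose care plans show person-centred approaches. It names no reference visit, no margin and no prior improvement.

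The analysis is given in two parts. The model: "LMMs will be used to compare changes in facility level measures from baseline to 24 months with facility included as random effects". Then: "Comparison of outcomes at 12 and 24 months will be examined to determine maintenance over that time period". The second part has no test, margin or rule for concluding.

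Four other places bear on this:

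- **Methods, Design** limits the 24-month assessment to one arm: "We will also examine Maintenance in EIT-4-BPSD facilities at 24 months post implementation". Procedure for Assessing Outcomes likewise places the 24-month setting measures in intervention sites only.
- **Adoption** (Aim 1) expects some facilities not to change, setting early and late adopters "versus those that are non-adopters (no change by 12 months"). The Maintenance criterion does not use these groups.
- **Attrition**, in the Maintenance paragraph: "We will track facilities that withdraw from the study within 12 months". Nothing specific is said about months 12 to 24.
- **Table 3** lists 24-month visits for Cohorts 1 and 2 (months 29 and 45) but only an 18-month visit for Cohort 3 (month 55).

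**The concern.** Maintenance should mean that a gain made during the intervention was kept. The plan's three elements each address something else. A facility with the same score at baseline, 12 and 24 months satisfies the criterion, whichever earlier visit is the reference. The baseline-to-24-month contrast stays positive if most of a gain is lost, for example up 6 items by month 12 and down 5 afterwards. The 12-versus-24-month comparison asks the right question, but without a margin it lets absence of a significant drop in a small sample stand as evidence of retention.

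The baseline-to-24-month change also has no concurrent control, while the Significance section describes pressure on all homes: "CMS has focused regulatory oversight on ensuring that care for residents with dementia is person-centered".

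Maintenance is one of the five RE-AIM criteria under Aim 1. The Innovation section motivates it by staff tending to return to old behaviours after an intervention ends. The plan as written could report maintenance when that had partly happened.

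**Working it through.** **1. The plan's own facility figure.** Sample Size gives effect size 0.9, 50 facilities and power above .90. With 25 per arm and two-sided 0.05, unadjusted power is 0.889 (normal) or 0.877 (t). With baseline adjustment it is 0.905 at a baseline–follow-up correlation of 0.3 and 0.974 at 0.6. The stated figure therefore reproduces with modest baseline adjustment. The plan gives no figure for Maintenance.

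**2. Facilities with 24-month data.** Cohorts start at months 5, 21 and 37. Adding 24 gives months 29, 45 and 61. The first two match Table 3; the third falls after the 60-month study. At 8–10 EIT-4-BPSD facilities per cohort, two cohorts give 16–20, and two thirds of 25 is 16.7. The range used is n = 16 to 25, before the 10% facility attrition the plan cites from prior work.

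**3. Can the 12-versus-24-month comparison detect loss of half the gain?** Assumptions: the 12-month gain is 0.9 baseline SDs (the plan's effect size); the correlation between visits is ρ = 0.6 (stated for residents, carried over to facilities); two-sided 0.05; paired t.

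- SD of a within-facility change: √(2(1 − 0.6)) = 0.894.
- Loss of half the gain: 0.45 SD. Non-centrality: 0.45 × √n / 0.894.
- n = 25: 2.516 against a critical value of 2.064. Chance of a non-significant decline: 33%.
- n = 16: 2.012 against 2.131. Chance: 53%.
- Across ρ from 0.3 to 0.8 and n from 16 to 25: 7% to 70%.
- Loss of the whole gain (ρ = 0.6): missed 0.2% of the time at n = 25 and 4% at n = 16.

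**4. What can the baseline-to-24-month contrast show without any intervention effect?** Same setting, with an assumed drift over time. The documents give no drift for these measures, so a range is shown.

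| Assumed drift (SD) | Significant rise, n = 25 | Significant rise, n = 16 |
|---|---|---|
| 0 | 2.5% | 2.5% |
| 0.2 | 19% | 13% |
| 0.3 | 36% | 24% |
| 0.45 | 68% | 47% |

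A concurrent EO comparison would hold this at 2.5% under any drift common to both arms.

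**5. Why the repair should not select facilities on an observed 12-month rise.** Take a never-changed facility with independent, equal scoring error of variance σ² at each visit. The apparent gain is e₁₂ − e₀, and the apparent amount kept is e₂₄ − e₀. Their covariance is σ² and the variance of the gain is 2σ², so the slope is 1/2. Pure error would look like 50% retention. Facility-level ratios are also unstable when the denominator is one item on a 24-item scale.

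**The case against.** The best defence is that the paragraph should be read whole. Its first sentence speaks of maintaining changes, so a facility with no change has nothing to maintain. Adoption reports non-adopters separately, the 12-month gain is tested against EO under H2, and the 12-versus-24-month comparison addresses the example of gaining 6 items and losing 5. That comparison would almost always detect loss of the whole gain. This shows good intent and narrows the point. It does not supply the missing condition or the missing margin: never-changers are also flat from 12 to 24 months, and partial loss is often missed.

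Three stronger readings are tempting and are not supported:

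- **That more non-adoption yields more maintenance.** This needs a count of facilities classed as maintained, which the plan never defines. In the named baseline-to-24-month model the reverse holds: non-adopters contribute zero change and pull the mean down. A significant rise there needs an observed gain, though not one attributable to EIT-4-BPSD.
- **That a known regulatory trend drives these scores.** The Significance section documents oversight and a 22% fall in antipsychotic use. It gives no trend in Environment, Policy or care-plan measures. Drift is plausible but of unknown size, and the Maintenance paragraph does not itself attribute the 24-month change to the intervention.
- **That facilities lost after month 12 are ignored.** The 12-month attrition sentence serves a comparison between arms. The general missing-data text plans to compare facilities that drop out and uses maximum likelihood under missing at random. What is absent is a statement of how such losses count towards Maintenance.

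**Conclusion.** The point stands as a defect in a stated rule. The criterion does not depend on a gain, the named contrast is not a measure of retention and is uncontrolled, and the one comparison that addresses retention has no margin. With 16 to 25 facilities, loss of half the gain would pass without a significant decline about 53% to 33% of the time. That rests on a 0.9 SD mean gain and ρ = 0.6; varying ρ from 0.3 to 0.8 widens the range to 7%–70%. The drift figures only illustrate why the baseline-to-24-month change cannot carry attribution; they do not estimate a bias in this trial. The plan should be changed before the 24-month data are analysed.

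**What to change.** For each measure (Environment, Policy, care-plan percentage):

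1. Fit one mixed model with baseline, 12 and 24 months over all EIT-4-BPSD facilities, without selecting on the observed 12-month rise.
2. Claim maintenance only if H2 shows a 12-month gain over EO and the 95% CI excludes a 12-to-24-month loss larger than a fraction f of the mean 12-month gain, with f fixed in advance. A linear contrast avoids a ratio: (mean₂₄ − mean₁₂) + f(mean₁₂ − mean₀), with its lower limit above zero.
3. Report descriptively, among EIT-4-BPSD facilities due a 24-month visit, the proportion that improved by month 12 and kept the improvement at month 24. Show never-changers separately, and count facilities that withdraw between 12 and 24 months as not maintained.
4. Label the baseline-to-24-month change as uncontrolled and not attributable to EIT-4-BPSD.
5. Reconcile the 24-month analysis with Table 3 for Cohort 3, and state the resulting number of facilities.

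Items 1 to 4 change analysis wording only. Item 5 may mean accepting fewer facilities or changing the schedule, so the 24-month data cannot all be taken as already planned.

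The price is a wider interval and a less favourable headline. As an illustration with f = 1/2 and ρ = 0.6 between every pair of visits, the contrast has SD √(1.5 × 0.4) = 0.775. Its 95% half-width is 2.064 × 0.775/√25 = 0.32 SD at n = 25 and 2.131 × 0.775/√16 = 0.41 SD at n = 16. Full retention of a 0.9 SD gain puts the contrast at 0.45, so on average the claim can just be made at n = 16, with little to spare.
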